10.2 Adverse Events

AEs will be summarized and presented using primary MedDRA System Organ Classes (SOCs) and preferred terms (PTs) according to the version of the MedDRA coding dictionary used for the study at the time of database lock. The actual version of the MedDRA coding dictionary used will be noted in the AE tables and in the clinical study report. Specific AEs will be counted once for each subject for calculating percentages,

unless stated otherwise. In addition, if the same AE occurs multiple times within a subject, the highest severity and level of relationship to study drug will be reported.

10.2.1 Treatment-Emergent Adverse Events and Newly Emergent Adverse Events

Treatment-emergent AEs (TEAEs) are defined as any AE with an onset date that is on or after the first dose of study treatment and no more than 30 days after the last dose of study drug. TEAEs for the DBP will be defined as any AE with an onset date that is on or after the first dose of DBP study drug and before the first dose of BEP study drug for subjects who participate in the BEP, or on or before the last dose of DBP study drug for subjects who participate in the Safety Follow-up Period (and not in BEP), or within 30 days after the last dose of DBP study drug for subjects who do not participate in either BEP nor Safety Follow-up Period. TEAEs for the BEP will be defined as any AE with an onset date that is on or after the first dose of BEP study drug and on or before the last dose of BEP study drug for subjects who participate in the Safety Follow-up Period, and within 30 days after the last dose of BEP study drug for subjects who do not participate in Safety Follow-up Period. AEs during Safety follow-up are defined as any AE with an onset date during the Safety Follow-up Period after the DBP and BEP. All TEAEs will be summarized overall, as well as by primary MedDRA SOC and PT. The SOCs will be presented in alphabetical order, and the PTs will be presented in alphabetical order within each SOC. All AEs during Safety follow-up will also be summarized in the same manner as TEAEs.

Unless otherwise specified, TEAEs will be summarized during the DBP and BEP, respectively, and AEs during Safety follow-up will be summarized during the Safety Follow-up Period.

The number and percentage of subjects experiencing TEAEs will be summarized. The number and percentage of subjects experiencing AEs during Safety follow-up will be summarized.

10.2.2 Adverse Event Overview

An overview of AEs will be presented consisting of the number and percentage of subjects experiencing at least one event for each of the following AE categories:

- Any TEAE/AEs during Safety follow-up
- Any TEAE/AEs during Safety follow-up with a reasonable possibility of being related to study drug according to the investigator
- Any severe TEAE/AEs during Safety follow-up
- Any serious TEAE/AEs during Safety follow-up
- Any TEAE leading to discontinuation of study drug (for the DBP and BEP)
- Any TEAE/AEs during Safety follow-up leading to death
- All deaths
- Deaths occurring \leq 30 days after last dose of study drug (for the Safety Follow-up Period only)
- Deaths occurring $>$ 30 days after last dose of study drug (for the Safety Follow-up Period only)
- Any TEAE/AEs during Safety follow-up of Special Interest

10.2.3 Treatment-Emergent Adverse Events by SOC and/or PT

TEAEs and AEs during Safety follow-up will be summarized by SOC and PT; SOC and PT with a reasonable possibility of being related to study drug as assessed by the investigator; by maximum severity and SOC and PT. Specific AEs will be counted once for each subject for calculating percentages, unless stated otherwise. In addition, if the same AE (SOC or PT) occurs multiple times within a subject, the highest severity and level of relationship to study drug will be reported.

In addition, TEAEs will be summarized by PT and treatment group (modal daily dose for BEP) and sorted by decreasing frequency for the total active group. AEs during Safety follow-up will also be summarized.

10.2.4 Deaths, Serious Adverse Events, and Adverse Events Leading to Study Drug Discontinuation

Treatment-emergent serious AEs (SAEs), TEAEs leading to premature discontinuation of study drug, and TEAEs leading to death will be summarized by SOC and PT and in listing format. AEs during Safety follow-up will also be summarized in the same manner as TEAEs except for AEs leading to premature discontinuation of study drug.

10.2.5 Adverse Events of Special Interest

AEs of special interest (AESIs) will be summarized overall and by PT and will be identified using the search criteria provided in Appendix B. Any extrapyramidal symptoms (EPS) TEAEs excluding akathisia/restlessness and any TEAE of akathisia/restlessness will also be summarized for the AESI of EPS.

Tabular listings of selected TEAEs of special interest will be provided.

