21. Subjects without gastric bypass or any condition that is expected to affect drug absorption.

22. No known history or current findings of convulsive disorders such as epilepsy (excluding history of infantile febrile convulsion without epileptiform findings), stroke, significant head injury, tumor of the central nervous system, or any other condition that predisposes the subject to a risk for seizures.

23. Subjects without any of the following conditions:

- A finding of cataracts (lens opacification[s] which meet Age-Related Eye Disease Study (AREDS) standard photo \geq #2) at the screening ophthalmological examination
- Any clinically significant ocular trauma or complications of ocular trauma, or history of retinal detachment, intraocular surgery (with the exception of cataract surgery to remove or replace lenses bilaterally) or laser treatment (except LASIK)
- History or current findings of ocular disease (e.g., open- or narrow-angle glaucoma, retinopathies, corneal diseases)
- History of any ocular diseases due to amiodarone or corticosteroid use in the past 3 years
- Intraocular pressure of > 21 mm Hg in either eye at the screening ophthalmological examination
- Unable to dilate pupil to at least 5 mm in either eye with the use of dilating eye drops

24. No history of tardive dyskinesia (except for mild cases attributed to use of conventional agents), serotonin syndrome, or neuroleptic malignant syndrome.

25. No history of syndrome of inappropriate antidiuretic hormone secretion.

26. No treatment history of any investigational product during the study or within 30 days or 5 half-lives of the drug (whichever is longer) prior to the first dose of study drug.

27. Subjects with ability to speak and understand the local language sufficiently to understand the nature of the study, to provide written informed consent, or to allow the completion of all study assessments as judged by the investigator (or subinvestigator).

- ✓ 28. No history of any malignancy within 5 years before randomization, except for successfully treated non-melanoma skin cancer or localized carcinoma in situ of the cervix.
- ✓ 29. No history of clinically significant (per investigator's [or subinvestigator's] judgment) **drug or alcohol abuse** within the last 6 months.
- ✓ 30. No conditions that could **interfere with drug absorption** including but not limited to short bowel syndrome.

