- The following are considered ocular AEs of special interest, whether serious or nonserious, and are required to be reported within 24 hours of the site being made aware:
 - cataract, lens, or lenticular abnormality or change, opacity, opacification or opalescence
 - blindness, night blindness, visual acuity or vision decrease, abnormality or change, visual acuity test abnormality or change
 - retinal, macular, or optic nerve degeneration, abnormality or change; retinal pigment epithelium detachment, abnormality or change

Adverse Event Severity and Relationship to Study Drug

The investigators will rate the severity of each AE as mild, moderate, or severe using the following definitions:

Mild	The AE is transient and easily tolerated by the subject.
Moderate	The AE causes the subject discomfort and interrupts the subject's usual activities.
Severe	The AE causes considerable interference with the subject's usual activities and may be incapacitating or life-threatening.

The investigator will use the following definitions to assess the relationship of the AE to the use of study drug:

Reasonable Possibility	After consideration of factors including timing of the event, biologic plausibility, clinical judgment, and potential alternative causes, there is sufficient evidence (information) to suggest a causal relationship.
-------------------------------	--

No Reasonable Possibility	After consideration of factors including timing of the event, biologic plausibility, clinical judgment, and potential alternative causes, there is insufficient evidence (information) to suggest a causal relationship.
----------------------------------	--

An AE is defined as any untoward medical occurrence, unintended disease or injury or any untoward clinical signs (including an abnormal laboratory finding) in subjects, users, or other persons whether or not related to the investigational medical device. This definition includes events related to the investigational medical device or comparator and events related to the procedures involved.

If an AE meets any of the following criteria, it is to be reported to AbbVie as an SAE within 24 hours after the site is made aware of the SAE:

- Led to death, injury, or permanent impairment to a body structure or body function
- Led to a serious deterioration in the health of a subject that either resulted in:
 - a life-threatening illness or injury, or
 - a permanent impairment of a body structure or a body function, or

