Appendix A. List of SAP Signatories

Name	Title	Role/Functional Area
		Author
		Author
		Clinical Statistics
		Statistical Programming
		Medical/Scientific Monitor

Appendix B. Definition of Adverse Events of Special Interest**Table B-1. AESI for Ocular Events with PTs**

AESI Category	MedDRA Preferred Terms (v 27.0)	Preferred Term Codes
Blindness	Amaurosis	10001902
	Amaurosis fugax	10001903
	Blindness	10005169
	Blindness day	10005178
	Blindness transient	10005184
	Blindness unilateral	10005186
	Diabetic blindness	10012646
	Sudden visual loss	10042441
Cataract	Atopic cataract	10069649
	Cataract	10007739
	Cataract cortical	10007748
	Cataract diabetic	10007749
	Cataract nuclear	10007759
	Cataract subcapsular	10007764
	Toxic cataract	10044135
Color vision decrease, abnormality or change	Chloropsia	10008585
	Chromatopsia	10008795
	Colour blindness	10010050
	Colour blindness acquired	10010051
	Colour vision tests abnormal	10010056
	Colour vision tests abnormal blue-yellow	10010057
	Colour vision tests abnormal red-green	10010058
	Cyanopsia	10051819
	Dyschromatopsia	10013892
	Erythropsia	10015290
Lens opacity, opacification or opalescence	Lens discolouration	10070549
	Lenticular opacities	10024214
	Posterior capsule opacification	10036346

AESI Category	MedDRA Preferred Terms (v 27.0)	Preferred Term Codes
Lens or lenticular abnormality	Acquired lenticonus	10064659
	Anterior capsular rupture	10081725
	Aphakia	10002945
	Lens disorder	10061219
	Posterior capsule neovascularisation	10081651
Macular degeneration, abnormality or change	Age-related macular degeneration	10064930
	Diffuse uveal melanocytic proliferation	10078228
	Dry age-related macular degeneration	10075567
	Macular cyst	10025407
	Macular degeneration	10025409
	Macular detachment	10075873
	Macular fibrosis	10071392
	Macular hole	10051058
	Macular opacity	10025416
	Macular pigmentation	10071041
	Macular rupture	10065319
	Macular thickening	10084571
	Maculopathy	10025425
	Neovascular age-related macular degeneration	10071129
	Pigmentary maculopathy	10054856
Night blindness	Delayed dark adaptation	10072729
	Night blindness	10029404
Optic nerve degeneration, abnormality or change	Myopic disc	10069088
	Optic atrophy	10030910
	Optic disc disorder	10061321
	Optic disc drusen	10030917
	Optic discs blurred	10030923
	Optic nerve cup/disc ratio decreased	10057513
	Optic nerve cup/disc ratio increased	10057567
	Optic nerve cupping	10030931
	Optic nerve disorder	10061322
	Papilloedema	10033712

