	Pseudopapilloedema	10037141

AESI Category	MedDRA Preferred Terms (v 27.0)	Preferred Term Codes
Retinal degeneration, abnormality or change	Acute macular neuroretinopathy	10086444
	Central serous chorioretinopathy	10086644
	Myopic chorioretinal degeneration	10079959
	Pars plana cyst	10034051
	Retinal cyst	10038839
	Retinal degeneration	10038845
	Retinal depigmentation	10038846
	Retinal deposits	10038847
	Retinal detachment	10038848
	Retinal disorder	10038853
	Retinal drusen	10062776
	Retinal dystrophy	10038857
	Retinal fibrosis	10071391
	Retinal infiltrates	10064833
	Retinal microangiopathy	10087077
	Retinal pallor	10038891
	Retinal pigment epithelial tear	10062971
	Retinal pigment epitheliopathy	10038893
	Retinal pigmentation	10038894
	Retinal tear	10038897
	Retinal thickening	10077890
	Retinal toxicity	10048955
	Retinal white without pressure	10079569
	Retinoschisis	10061492
	Rhegmatogenous retinal detachment	10065569
	Serous retinal detachment	10040114
	Subretinal fibrosis	10062958
	Subretinal fluid	10069356
	Subretinal hyperreflective exudation	10082240
	Tractional retinal detachment	10080316

AESI Category	MedDRA Preferred Terms (v 27.0)	Preferred Term Codes
Retinal pigment epithelium detachment, abnormality or change	Acquired hypertrophy of the retinal pigment epithelium	10086462
	Chorioretinal disorder	10061763
	Chorioretinopathy	10063118
	Detachment of macular retinal pigment epithelium	10071004
	Detachment of retinal pigment epithelium	10052501
	Retinal dystrophy	10038857
Vision decreased, abnormality or change	Accommodation disorder	10000389
	Acute myopia	10078300
	Altered visual depth perception	10053549
	Aniseikonia	10002534
	Anisometropia	10002537
	Antimetropia	10059397
	Astigmatism	10003569
	Cortical visual impairment	10076660
	Delayed light adaptation	10079805
	Hemianopia	10019452
	Hemianopia heteronymous	10019455
	Hypermetropia	10020675
	Low luminance best-corrected visual acuity decreased	10074928
	Myopia	10028651
	Pathologic myopia	10073286
	Presbyopia	10036628
	Pseudomyopia	10075919
	Quadrantanopia	10077820
	Tunnel vision	10045178
	Visual field defect	10047555
	Visual impairment	10047571
	Visual snow syndrome	10079450
Visual acuity decreased, abnormality or change	Refraction disorder	10038264
	Visual acuity reduced	10047531
	Visual acuity reduced transiently	10047532

AESI Category	MedDRA Preferred Terms (v 27.0)	Preferred Term Codes

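### Ocular AESIs are identified only from a closed preferred-term list that is narrower than the protocol's definition: it has no term for blurred vision or plain retinopathy

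*SAP*

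**What the plan says.** Protocol 6.1, under Adverse Events of Special Interest, makes certain eye events AESIs whether or not they are serious, and asks sites to report them within 24 hours. The events are described by concept, not by dictionary term. For vision the wording is "blindness, night blindness, visual acuity or vision decrease, abnormality or change, visual acuity test abnormality or change". For the back of the eye it is "retinal, macular, or optic nerve degeneration, abnormality or change; retinal pigment epithelium detachment, abnormality or change". A further item covers the lens.

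SAP 10.2.5 says that AESIs "will be identified using the search criteria provided in Appendix B". For eye events the criteria are Table B-1 in SAP Appendix B, titled "AESI for Ocular Events with PTs". It lists individual MedDRA 27.0 preferred terms with their codes, under headings that largely follow the protocol's concepts, for example "Vision decreased, abnormality or change" and "Retinal degeneration, abnormality or change".

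The SAP describes no other way for an event to become an AESI. There is no site flag, no higher-level dictionary grouping and no medical review step. The AESI classification feeds one line of the overview in SAP 10.2.2, and the tables and listings in SAP 10.2.5. SAP 13.1, which lists changes from the protocol's planned analyses, mentions no change to the AESI definition.

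**The concern.** An open definition in the protocol is turned into a closed list in the SAP. That works only if the list holds every term to which a qualifying event could be coded. Two everyday candidates are absent: blurred vision, which on a plain reading is an abnormality or change of vision, and retinopathy without further qualification, which is a retinal abnormality.

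What is at stake is agreement between what sites are told to report as an ocular AESI and what the study report counts as one. An event could meet the protocol definition, be reported within 24 hours as an AESI, and then not be counted in the AESI output.

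**Working it through.** The documents state no figure on this point, so there is none to reproduce. The check compares Table B-1 with the protocol's concepts.

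**Inputs.** The concept wording comes from Protocol 6.1, the identification rule from SAP 10.2.5, the term list from SAP Appendix B, Table B-1, and the number randomized (34) from SAP 1.0.

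**Step 1: size of the list.** The rows per category, in table order, are blindness 8, cataract 7, color vision 10, lens opacity 3, lens abnormality 5, macular 15, night blindness 2, optic nerve 11, retinal 30, retinal pigment epithelium 6, vision 22, visual acuity 3 and visual acuity test 2. The sum is 8 + 7 + 10 + 3 + 5 + 15 + 2 + 11 + 30 + 6 + 22 + 3 + 2 = 124 rows in 13 categories. Retinal dystrophy appears twice, so there are 123 distinct terms.

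**Step 2: search for the two terms.**

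| Search | Hits in Table B-1 |
|---|---|
| contains blur | 1: "Optic discs blurred", an optic-disc finding |
| contains retinopathy | 3: acute macular neuroretinopathy, central serous chorioretinopathy, chorioretinopathy |
| exactly retinopathy | 0 |
| exactly vision blurred or blurred vision | 0 |

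**Step 3: could the gap come from text extraction?** This is unlikely. Within each category the terms run alphabetically. Plain retinopathy would sort between retinal white without pressure and retinoschisis. A term starting with the word vision would sort between tunnel vision and visual field defect. Both places lie inside unbroken runs, not at a page break or a redaction.

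**Step 4: do the two events fall within the protocol's concepts?** Protocol 6.1 names neither. Its wording is open, however, and both fit it on a plain reading. Eligibility criterion 23 is not an AESI definition, but it shows that the protocol regards retinopathies as ocular disease. A deliberate choice to keep the list specific does not explain the gaps well, because the list admits presbyopia, astigmatism, myopia, maculopathy and chorioretinopathy.

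**Step 5: what happens to an unlisted event?** It does not count in the AESI line of SAP 10.2.2 or in the tables and listings of SAP 10.2.5. It does appear in the tables of SAP 10.2.3 by system organ class and preferred term.

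**Step 6: scale.** The number of such events cannot be estimated from the documents. Arm sizes are not given either. Purely as an illustration, suppose the 34 randomized subjects were split evenly over two or three double-blind groups (the SAP includes the former 3 mg/day group). That gives 34/2 = 17 or 34/3 ≈ 11 per group. One subject is then 1/17 = 5.9 or 1/11 = 9.1 percentage points of a group's incidence, and more in a smaller group. This shows how coarse the table is. It is not an estimate of loss.

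**The case against.** The strongest reply is that the harm depends on coding that cannot be seen. MedDRA is not in the documents, and the list holds broad terms that might receive such reports: visual impairment, visual acuity reduced, retinal disorder. An event coded to one of these is captured. The list is also maintained, since the SAP version history records updates for MedDRA 26.0 and 27.0, and every protocol concept has a category. On this view the dispute is only about the choice of terms. The first part stands: the loss is conditional. The second does not remove the gap, because a category heading captures nothing unless the term itself is listed.

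A second reply is that eye safety is covered elsewhere. SAP 10.5.2 summarizes visual acuity, and Table C-6 flags a logMAR change of at least 0.3. That is true and it limits the consequence. It does not close the gap, because milder or transient blurring need not reach that threshold. The activity schedule in Protocol Appendix D places slit-lamp examination in screening only, with acuity alone thereafter. After baseline, retinal findings would therefore reach the analysis mainly as adverse events.

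A reader might go further and infer that protocol-defined AESIs will certainly drop out, that the counts will disagree with the safety database, or that the eye-safety conclusion is read from the AESI output alone. The documents support none of these. Coding is unknown, the safety database and any reconciliation are not described, and no section says which output carries the eye-safety conclusion. Nor is it right that site reports are ignored: reported events are coded and counted whenever their term is listed. What is missing is a separate route for events that the site classed as ocular AESIs.

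**Conclusion.** The point holds in a limited form. The SAP's rule for ocular AESIs is narrower than the protocol's definition, and the SAP does not list this as a change. The absence of both terms is a fact of Table B-1.

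The consequence rests on two assumptions: that such an event occurs, and that it is coded to a term outside the list. If both hold, the event is misclassified in the AESI overview line, tables and listing. It is not lost from the report. Frequency and size cannot be derived. To say that the list captures none of the unlisted events is true by definition and measures nothing. The study ended early, its safety analysis is descriptive and it feeds an abbreviated report, so the effect is confined to descriptive AESI output. The correction is still worth making, because it is cheap and removes a mismatch between the two documents.

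**What to change.** Before database lock:

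1. Review Table B-1 against each ocular concept in Protocol 6.1, and add the MedDRA 27.0 preferred terms and codes for blurred vision and for retinopathy.
2. Reword SAP 10.2.5 along these lines: *Ocular AESIs are all adverse events whose preferred term is in Table B-1, together with all adverse events that the site reported as ocular AESIs under Protocol Section 6.1, where that report is available in the clinical data. Events identified by the preferred-term list alone are also shown in a separate row.*
3. Record the change in the SAP version history.

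The cost is a wording change, two added terms and, if the site's classification is held in the clinical data, one further condition in the AESI derivation. The documents do not show whether that field exists. If it does not, the term review stands alone. There are two downsides. Some non-specific events, such as transient blurring, will enter the ocular table, and the site-reported route depends on how each site classifies events. The list-only row keeps a count that does not depend on site classification. For comparison with earlier work based on the existing list, that row should mark the newly added terms.

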10.3 Analysis of Laboratory Data

The clinical laboratory tests defined in the protocol operations manual (e.g., hematology, clinical chemistry, and urinalysis) will be summarized.

Each continuous laboratory variable will be summarized for all time points (starting with Baseline) with the number of non-missing observations, mean and standard deviation, median, minimum and maximum. Mean change from baseline to each planned time point and to the minimum, maximum, and final post-baseline value will be summarized with the number of observations, baseline mean, and visit mean. The change from baseline mean, standard error, and 95% confidence interval will be presented for the mean change from baseline within each treatment group (modal daily dose for BEP).

Changes in laboratory parameters will be tabulated using shift tables categorized as low, normal, or high based on the normal ranges of the laboratory used for each sample. A shift table will be provided to summarize shifts from baseline to the final post-baseline value.

The criteria for potentially clinically significant (PCS) laboratory values will be determined by list in Appendix C. For each laboratory PCS criterion, the number and percentage of subjects who have at least 1 post-baseline observation that meets the PCS criterion and is more extreme than their baseline value will be summarized by treatment group (modal daily dose for BEP). Listings of subject-level laboratory data will be provided for subjects meeting the criteria.

